Dosage/Dose Regimen:	Subjects eligible to be randomized will receive one of the following treatments to be administered bilaterally as 1-2 drops █████ for 56 days (from Visit 2 to Visit 5): 1) 1.55 µg/mL SkQ1 ophthalmic solution 2) Placebo SkQ1 ophthalmic solution (Vehicle) During a 7-day study run-in period (beginning at the end of Visit 1 for the purpose of subject selection) prior to randomization, all subjects will receive 1-2 drops of Placebo SkQ1 ophthalmic solution (Vehicle) bilaterally █████
Summary of Visit Schedule:	5 visits over the course of approximately 9 weeks 
 • Visit 1 = Day -7 -2/+1 days, Screening • Visit 2 = Day 1, Baseline, Screening Confirmation, Randomization and Initiation of Double-Masked Treatment • Visit 3 = Day 29 ± 2 days • Visit 4 = Day 43 ± 2 days

	
 • Visit 5 = Day 57 ± 4 days, 8-Week CAE[®] Test, End of Double-Masked Treatment • [REDACTED]

Measures Taken to Reduce Bias:
	
This is a double-masked study. Subjects will be assigned to treatment groups using stratified random sampling [REDACTED]

Study Population Characteristics
	

Number of Subjects:
	
Approximately [REDACTED] subjects will be screened to enroll approximately 600 (300 active : 300 placebo) subjects

Condition/Disease:
	
Dry Eye Syndrome

Inclusion Criteria:
	
Subjects must:
 
 a. Be at least 18 years of age; b. Provide written informed consent; c. Have a subject-reported history of dry eye for at least 6 months prior to Visit 1; d. Have a history of use or desire to use eye drops for dry eye symptoms within 6 months of Visit 1; e. [REDACTED] f. [REDACTED] g. [REDACTED] h. [REDACTED] i. [REDACTED]

	
j. [REDACTED]
 
k. Have at least one eye (the same eye) satisfy all criteria for f, g, h, i, and j above.

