[REDACTED] Sensitivity analyses for the ocular discomfort endpoint will also be performed using Last Observation Carried Forward (LOCF) method on the ITT population as well as with the observed data only for both the ITT and PP populations. Sensitivity analyses for the conjunctival fluorescein staining endpoint will be performed using LOCF on the ITTCFS population as well as with the observed data only for both the ITTCFS and PPCFS populations. Sensitivity analyses using LOCF and observed data only will include Wilcoxon rank sum tests.

Key Secondary Efficacy Analyses

The key secondary efficacy endpoint of conjunctival fluorescein staining at Visit 4 (Day 43) will be tested in the ITTCFS population; other key secondary efficacy endpoints will be tested in the full ITT population.

Imputation will not be applied for any missing data in the key secondary efficacy endpoints.

Analyses will use ANCOVA models with baseline values included as covariates. Two-sample t-tests and Wilcoxon rank sum tests will be performed as sensitivity analyses.

Sensitivity analyses of the conjunctival fluorescein staining endpoint will be performed using the PPCFS population with observed data only. Sensitivity analyses of the other key secondary endpoints will be performed using the PP population with observed data only.

Exploratory Efficacy Analyses

Exploratory efficacy analyses will be analyzed on the ITT population using observed data. Imputation will not be applied for any missing data in the exploratory efficacy endpoints.

Analyses will use ANCOVA models with baseline values included as covariates, two-sample t-tests, and Wilcoxon rank sum tests. [REDACTED]

Safety Variables

Frequencies and percentages of subjects with treatment-emergent adverse events (TEAEs), serious TEAEs, and TEAEs causing premature treatment discontinuation will be provided by treatment group. An AE is treatment emergent if it occurs or worsens

after the first dose of study treatment. Furthermore, frequencies will be given of subjects with TEAEs by system organ class and preferred term for the following categories of AEs:

- All TEAEs
- TEAEs at least possibly related to study treatment
- TEAEs leading to study treatment discontinuation
- Serious TEAEs (SAEs)
- By maximal severity
- By study day of onset

Separate analyses will be performed for ocular and non-ocular AEs.

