5 STUDY POPULATION

5.1 Number of Subjects (approximate)

It is estimated that approximately [REDACTED] subjects will be screened to enroll approximately 600 (300 active: 300 placebo) subjects. Subjects will be randomized in a 1:1 ratio to 1.55 µg/mL SkQ1 or placebo.

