8.1.4 Procedures for Final Study Entry

Subjects must meet all inclusion and none of the exclusion criteria.

8.1.5 Methods for Assignment to Treatment Groups:

Prior to initiation of study run-in (at Visit 1), each subject who signs the informed consent will be assigned a screening number. All screening numbers will be assigned in strict numerical sequence at each site and no numbers will be skipped or omitted.

At Visit 2, a patient who meets all the eligibility criteria will be randomized to receive treatment with 1.55 µg/mL SkQ1 Ophthalmic Solution or placebo in a 1:1 ratio [REDACTED]

Subjects will be assigned to treatment groups using stratified random sampling and stratification [REDACTED]

[REDACTED]

[REDACTED] The site staff will dispense to the patient the study kit labeled with the corresponding kit number. Both the randomization number and the dispensed study drug kit number will be recorded on the patient's source document and eCRF. Kit numbers for returned bottles will also be recorded for each visit.

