10.4.4 Multiplicity Adjustments

The primary and key secondary efficacy analyses will be tested following a hierarchical testing strategy in order to maintain a study-wide type I error rate of 0.05 while testing the primary and key secondary hypotheses. The testing strategy will proceed as follows:

- 1) Compare the change from baseline in Ocular Discomfort at Visit 5 (Day 57) [REDACTED] between SkQ1 and placebo. If statistically significant at a two-sided $\alpha = 0.05$, proceed to step 2; otherwise no further testing will be performed and all other testing is considered exploratory.
- 2) Compare the change from baseline in conjunctival fluorescein staining (sum of temporal and nasal regions) at Visit 5 (Day 57) [REDACTED] in the worst eye between SkQ1 and placebo. [REDACTED] If statistically significant at a two-sided $\alpha = 0.05$, proceed to step 3; otherwise no further testing will be performed and all other testing is considered exploratory. Compare the change from baseline in Ocular Discomfort at Visit 3 (Day 29) [REDACTED] between SkQ1 and placebo. If statistically significant at a two-sided $\alpha = 0.05$, proceed to step 4; otherwise no further testing will be performed and all other testing is considered exploratory.
- 3) Compare the change from baseline in conjunctival fluorescein staining (sum of temporal and nasal regions) at Visit 4 (Day 43), [REDACTED] between SkQ1 and placebo. [REDACTED] If statistically significant at a two-sided $\alpha = 0.05$, proceed to step 5; otherwise no further testing will be performed and all other testing is considered exploratory.

- 4) Compare the tear film break-up time pre- to post-CAE[®] change at Visit 5 (Day 57) in the worst eye between SkQ1 and placebo. If statistically significant at a two-sided alpha = 0.05, proceed to step 6; otherwise no further testing will be performed and all other testing is considered exploratory.
- 5) Compare the change from baseline in corneal fluorescein staining in the central region at Visit 3 (Day 29) [REDACTED] [REDACTED] between SkQ1 and placebo. All other testing is considered exploratory.

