10.4.5 Primary Efficacy Analyses

Primary efficacy endpoints are:

- Change from baseline (Visit 2) in Ocular Discomfort in the study worst eye at Visit 5 (Day 57) [REDACTED]
- Change from baseline (Visit 2) in conjunctival fluorescein staining (sum of temporal and nasal regions) in the study worst eye at Visit 5 (Day 57) [REDACTED]

[REDACTED]

The primary efficacy endpoints will be analyzed using an analysis of covariance (ANCOVA) model, [REDACTED]. The adjusted least squares means and their standard errors (SEs) will be presented along with their two-sided 95% confidence intervals (CIs) for each treatment group and the difference between the active treatment group and the placebo treatment group. In addition, a two-sample t-test will be used to compare the active and placebo groups in the change from baseline at Visit 5 [REDACTED]. The mean difference, SD for the difference, and the 95% CI for the difference will be presented. A two-sided p-value < 0.05 will be considered statistically significant.

The primary analyses for both primary endpoints will be conducted on the ITT and ITTCFS populations for Ocular Discomfort and conjunctival fluorescein staining, respectively, using the Markov Chain Monte Carlo (MCMC) multiple imputation method to impute missing data. [REDACTED]

[REDACTED] Sensitivity analyses for the ocular discomfort endpoint will also be performed using Last Observation Carried Forward (LOCF) method on the ITT population as well as with the observed data only for both the ITT and PP populations. Sensitivity analyses for the conjunctival fluorescein staining endpoint will be

performed using LOCF on the ITTCFS population as well as with the observed data only for both the ITTCFS and PPCFS populations. Sensitivity analyses using LOCF and observed data only will include Wilcoxon rank sum tests.

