10.4.6 Key Secondary Efficacy Variables

The key secondary efficacy endpoint of conjunctival fluorescein staining at Visit 4 (Day 43) will be tested in the ITTCFS population; other key secondary efficacy endpoints will be tested in the full ITT population.

Imputation will not be applied for any missing data in the key secondary efficacy endpoints.

Analyses will use ANCOVA models with baseline values included as covariates. Two-sample t-tests, and Wilcoxon rank sum tests will be performed as sensitivity analyses.

Sensitivity analyses of the conjunctival fluorescein staining endpoint will be performed using the PPCFS population with observed data only. Sensitivity analyses of the other key secondary endpoints will be performed using the PP population with observed data only.

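### Randomisation is stratified, but the key secondary ANCOVA names only baseline values as covariates; if the strata predict outcome beyond baseline, the H03 to H06 tests are conservative and lose a little power

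*Combined protocol and SAP*

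**What the plan says.** The synopsis (Measures Taken to Reduce Bias) states "Subjects will be assigned to treatment groups using stratified random sampling", and section 8.1.5 repeats it: "Subjects will be assigned to treatment groups using stratified random sampling and stratification". The factors and the block design are redacted. The allocation ratio is 1:1 (section 5.1).

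For the key secondary endpoints, section 10.4.6 gives the model in one sentence: "Analyses will use ANCOVA models with baseline values included as covariates". The next sentence follows directly: "Two-sample t-tests, and Wilcoxon rank sum tests will be performed as sensitivity analyses". The Key Secondary Efficacy Analyses paragraph of the synopsis carries the same text. Neither place shows a redaction, and neither mentions the stratification factors.

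The primary analysis reads differently. In section 10.4.5, "The primary efficacy endpoints will be analyzed using an analysis of covariance (ANCOVA) model" is followed by a redaction where a covariate list would stand. The exploratory section (10.4.7) also has a redaction after its model sentence. Nothing is claimed here about the covariates of those two analyses.

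The key secondary hypotheses H03 to H06 belong to the fixed sequence that controls the study-wide error rate at 0.05 (sections 10.2 and 10.4.4). After a non-significant step, "otherwise no further testing will be performed and all other testing is considered exploratory".

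**The concern.** Stratified allocation balances the factors between arms, so they contribute almost nothing to the true variance of the treatment difference. A model that omits them does not know this. It leaves whatever outcome variance they explain in the residual and reports a standard error larger than the real one. The test then rejects too rarely under the null and has less power than a model that analyses as the trial was randomised.

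What is at stake is efficiency, not validity. It matters somewhat more than for free-standing secondary endpoints because the sequence stops at the first failure: a miss at H03 caused by an over-wide standard error also ends formal testing of H04, H05 and H06.

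**Working it through.** **Inputs from the documents.** Two-sided alpha 0.05 (section 10.2); 1:1 allocation with 300 per arm planned (Synopsis; section 5.1); 284 per group for 90% power for each endpoint (section 10.3); stratified randomisation (section 8.1.5); key secondary model with baseline values as covariates and no imputation (section 10.4.6).

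**Assumptions.** The stratification factors, effect sizes and standard deviations are redacted, and no power is stated for H03 to H06. Let R² be the share of residual variance, after baseline, that the strata explain. It is taken as 5%, 10% or 15%. Nominal power of 90% and 80% serves as two illustrative settings.

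**The plan's own figure.** The 284 per group cannot be reproduced independently because its inputs are redacted. Solving backwards, it implies a standardised effect of (1.960 + 1.282) × √(2/284) = 0.272, for which 300 per arm would give 91.5% power. Section 10.3 frames this calculation around the primary variables, so it is used only as a reference in the second simulation below.

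**Formulas.** With balance within strata, the true standard error is s = √(1 − R²) times the one the model reports. Let d = 1.960 + z(nominal power), so d = 3.242 at 90% and 2.802 at 80%. Then:

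- reported SE / true SE = 1/s
- true type I error without strata = 2[1 − Φ(1.960/s)]
- power without strata = Φ((d − 1.960)/s)
- power with strata = Φ(d/s − 1.960)

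For R² = 10% at nominal 90%: s = √0.90 = 0.9487. Type I error is 2[1 − Φ(2.066)] = 3.9%. Power is Φ(1.282/0.9487) = Φ(1.351) = 91.2% without strata and Φ(3.242/0.9487 − 1.960) = Φ(1.457) = 92.7% with them.

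| R² | SE too large by | Type I error, no strata | Power at nominal 90%: without → with | Loss (points) | Power at nominal 80%: without → with | Loss (points) |
|---|---|---|---|---|---|---|
| 5% | 2.6% | 4.4% | 90.6% → 91.4% | 0.8 | 80.6% → 82.0% | 1.4 |
| 10% | 5.4% | 3.9% | 91.2% → 92.7% | 1.6 | 81.3% → 84.0% | 2.7 |
| 15% | 8.5% | 3.4% | 91.8% → 94.0% | 2.2 | 81.9% → 86.0% | 4.0 |

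Losses are taken from unrounded values.

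**Simulation checks.**

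1. 600 subjects, ten equal strata independent of baseline, permuted blocks of 4 (assumed), 40,000 runs per setting. Type I error without strata was 4.4%, 3.8% and 3.4% for the three R² values, against 5.0% with strata. Power was 90.3%, 90.9% and 91.5% without and 91.1%, 92.6% and 93.9% with.
2. 300 per arm, eight strata, blocks of 4, standardised effect 0.272, 10,000 runs. At R² of 5%, 10% and 20%, type I error without strata was 4.3%, 3.6% and 3.1%, and power without against with strata was 92.0% vs 92.7%, 92.5% vs 94.0% and 93.9% vs 96.2%. Direction and size agree.

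**Cases where little or nothing is gained (8,000 runs each).** With strata defined as a median split of the baseline score already in the model, power was 89.8% without and 89.7% with them, a difference within Monte Carlo error of about 0.3 points. With ten strata that explain nothing, power was 89.7% both ways.

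**Accumulation along the sequence, as illustration only.** If H03 to H06 were four independent tests at nominal 90%, the chance of passing all four would be the fourth power of the single-test figure: 67.3%, 69.1% or 70.9% without strata, against 69.8%, 74.0% or 78.1% with them. The endpoints are probably correlated, which would shrink these gaps.

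**The case against.** The strongest reply is that the deciding fact is redacted. If the strata are categories of a score already in the model, nothing is lost, and a reader cannot tell whether this trial is in that case. This stands as a limit: the finding is conditional, and no loss can be demonstrated from the public text.

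Second, the phrase about baseline values is plural and not exclusive, so it might be meant to cover stratification factors fixed by Visit 2. That reading is possible, but the text does not say so. A confirmatory model should not depend on it.

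Third, redactions elsewhere might name the factors. Section 10.4.1 has one after its definition of baseline, and section 10.4.4 has several in the steps for H03, H04 and H06. Those in 10.4.4 sit where endpoint or population descriptors belong rather than in a model statement. The one in 10.4.1 leaves some residual doubt.

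Fourth, the loss is forgone gain rather than a shortfall: in the table, power without strata is never below nominal. That is correct, and it keeps the grade low.

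Fifth, the calculation does not fit all four tests equally well. H04 uses the ITTCFS subset, whose size and definition are not visible. If its criterion were also a stratification factor, that factor would be constant within the subset and adjusting for it would gain nothing. All four tests use observed data, so balance within strata need not be exact. These points affect the size for individual tests, not the direction.

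**Conclusion.** The concern holds. Randomisation is stratified, and the visible key secondary model leaves the stratification factors out, with no redaction at that point to explain it. The consequence is conservative tests and a modest loss of power relative to the adjusted model: 0.8 to 2.2 points per test at nominal 90%, or 1.4 to 4.0 at nominal 80%, for strata explaining 5% to 15% of the residual variance. Those shares, the number of strata and the block size are assumptions. The loss may be close to zero if the strata only categorise baseline. There is no inflation of type I error and no shortfall against the 90% in section 10.3. This is an improvement the sponsor should make, with medium confidence; it is not a flaw that threatens the trial's conclusions.

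**What to change.** In section 10.4.6 and the matching synopsis paragraph, state that the key secondary ANCOVA includes the randomisation stratification factors as well as the baseline covariate already named. If the factors are already meant to fall under baseline values, say so explicitly. Make the change before unmasking, because covariates added later would look data-driven.

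The cost is one sentence in two places, no new data and a few degrees of freedom (9 with ten strata). When the strata explained nothing, adjusting for ten of them cost less than 0.1 point of power in simulation. The sponsor knows the factors and can see at once how many levels there are, including within the ITTCFS subset used for H04.

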6.1.2 Key Secondary Efficacy Measures

The key secondary efficacy endpoints will be tested in a hierarchical fixed sequence in the following order:

1. Change from baseline (Visit 2) in Ocular Discomfort at Visit 3 (Day 29) [REDACTED]
2. Change from baseline (Visit 2) in conjunctival fluorescein staining (sum of temporal and nasal regions) at Visit 4 (Day 43) [REDACTED]
3. Tear film break-up time pre- to post- CAE[®] at Visit 5 (Day 57) in the worst eye at baseline;
4. Change from baseline (Visit 2) in corneal fluorescein staining in central region at Visit 3 (Day 29) [REDACTED]

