8.3 Examination Procedures

8.3.1 Procedures to be Performed at Each Study Visit with Regard to Study Objective(s)

The following procedures will be performed (see Appendix 2 for description):

Visit 1 (Day -7 -2/+1 days): Screening

- Informed consent / Health Information Portability and Accountability Act (HIPAA);
- Demographic data and medical / medication history;
- Urine pregnancy test (for females of childbearing potential);
- [REDACTED] Ocular Discomfort Scale;
- [REDACTED] Ocular Discomfort Scale & 4-Symptom Questionnaire;
- [REDACTED]
- Visual acuity;
- Review of qualification criteria;
- Slit-lamp biomicroscopy;
- [REDACTED] [REDACTED]
- [REDACTED]
- Tear Film Break-up Time (TFBUT);
- Fluorescein staining [REDACTED]

- [REDACTED];
- [REDACTED]
- [REDACTED]
- Intraocular pressure;
- Dilated funduscopy;
- Review of qualification criteria;
- Adverse event query;
- Dispensation of run-in (RUN-IN) for [REDACTED] until Visit 2;
 - [REDACTED]
- [REDACTED]
 - [REDACTED]
- Dispensation of diaries and subject instructions;
 - [REDACTED]
 - [REDACTED]
 - [REDACTED]
 - [REDACTED]
- Qualified subjects will be scheduled for Visit 2.

Visit 2 (Day 1): Baseline/Screening Confirmation/ Randomization and Initiation of Double-Masked Treatment

- Collection and review of run-in (RUN-IN) and subject diaries;
- [REDACTED]
- Medical/medication history update;
- Adverse event query;
- [REDACTED] Ocular Discomfort Scale;

- [REDACTED] Ocular Discomfort Scale & 4-Symptom Questionnaire;
- [REDACTED]
- Visual acuity;
- Slit-lamp biomicroscopy;
- [REDACTED]
- [REDACTED]
- TFBUT;
- Fluorescein staining [REDACTED]
- [REDACTED] [REDACTED]
- [REDACTED]
- [REDACTED]
- Review of qualification criteria;
- Randomization;
- Dispensation of study drug kit according to randomization for [REDACTED] until Visit 3;
- [REDACTED]
 - [REDACTED]
- [REDACTED]
- [REDACTED]
- [REDACTED]
 - [REDACTED]
 - [REDACTED]
 - [REDACTED]
- Adverse event query;
- Schedule subjects for Visit 3.

○ [REDACTED]

- Adverse event query;
- Schedule subjects for Visit 4.

[REDACTED]

■ [REDACTED]

Visit 4 (Day 43 ± 2 days): 4-Week Follow-up

- Collection and review of study drug and subject diaries;
- [REDACTED]
- Medical / medication history update;
- Adverse event query;
- [REDACTED] Ocular Discomfort Scale;
- [REDACTED] Ocular Discomfort Scale & 4-Symptom Questionnaire;
- [REDACTED]
- Visual acuity;
- Slit-lamp biomicroscopy;
- [REDACTED] [REDACTED]
- [REDACTED]
- TFBUT;

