10.4 Statistical Analysis

10.4.1 General Considerations

The quantitative variables will be summarized using mean, median, standard deviation (SD), minimum and maximum. The qualitative variables will be summarized using counts and percentages.

All efficacy analyses will be evaluated at a two-sided $\alpha = 0.05$ and two-sided 95% CIs around the difference between treatments (SkQ1 – placebo) as well as two-sided 95% CIs around the point estimates within each treatment group.

All summaries will be presented by treatment group. Summaries will be provided for demographics, baseline medical history, and subject disposition.

Baseline measures are defined as the last measure prior to the initiation of study treatment (Visit 2). [REDACTED]

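### The key secondary ANCOVAs adjust for the Visit 2 value only; adding the Visit 1 value, already collected, would probably sharpen three of the four at almost no cost

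*Combined protocol and SAP*

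**What the plan says.** Section 10.4.6 (Key Secondary Efficacy Variables) carries no redaction. Its model statement is "Analyses will use ANCOVA models with baseline values included as covariates", and it names no other covariate. Missing key secondary data are not imputed.

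Section 10.4.1 (General Considerations) fixes the meaning of baseline: "Baseline measures are defined as the last measure prior to the initiation of study treatment (Visit 2"). A redacted run follows that sentence.

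Section 8.3.1 lists the assessments by visit. Under "Visit 1 (Day -7 -2/+1 days): Screening" it includes the "Ocular Discomfort Scale & 4-Symptom Questionnaire", tear film break-up time (TFBUT) and fluorescein staining. All three appear again at Visit 2, ahead of the randomisation step. Between the two visits every subject has a 7-day vehicle run-in, described in the synopsis as "beginning at the end of Visit 1 for the purpose of subject selection".

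Section 6.1.2 lists four key secondary endpoints. Three are changes from Visit 2: Ocular Discomfort at Day 29, conjunctival fluorescein staining at Day 43 and central corneal fluorescein staining at Day 29. The third in the sequence is of a different kind: "Tear film break-up time pre- to post- CAE[®] at Visit 5 (Day 57) in the worst eye at baseline".

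**The concern.** A single symptom score or staining grade is a noisy reading of a subject's underlying level. A second reading taken before randomisation usually carries further information on that level. For three key secondary endpoints such a reading is already scheduled, but the model as written does not use it.

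What is at stake is precision, not validity. A prespecified pre-randomisation covariate does not bias the treatment comparison, and where it predicts the outcome beyond Visit 2 it narrows the confidence interval. Sections 10.2 and 10.4.4 test the key secondaries in a fixed sequence after both primaries, and one non-significant result ends formal testing. A modest gain at an early step therefore also helps the steps behind it.

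**Working it through.** **Step 1. Is there a Visit 1 counterpart?** Sections 6.1.2 and 8.3.1 side by side:

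| Key secondary endpoint | Visit 1 value of the same measure visible? |
|---|---|
| Ocular Discomfort, Day 29 | Yes |
| Conjunctival staining, Day 43 | Yes, if the redacted scale and regions match |
| TFBUT, pre- to post-CAE within Visit 5 | No. TFBUT is visibly listed twice at Visit 5 but once each at Visits 1 and 2 |
| Central corneal staining, Day 29 | Yes, if the redacted scale and regions match |

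**Step 2. The plan's own figure.** Section 10.3 gives 284 per group for 90% power, two-sided 0.05. Its effect sizes and SDs are redacted, so it cannot be reproduced. Inverting it gives a standardised difference of (1.960 + 1.2816) × √(2/284) = 0.272. This is a back-calculation, not a check, and it concerns the primary variables. No power is visible for any key secondary endpoint.

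**Step 3. Formulas.** Let c be the Visit 1–Visit 2 correlation, b the Visit 2–outcome correlation and a the Visit 1–outcome correlation. As a fraction of the outcome variance, the residual variance is

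- Visit 2 only: 1 − b²
- both visits: 1 − (a² + b² − 2abc)/(1 − c²)

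The ratio of the second to the first measures the gain. It equals 1 (no gain) when a = bc. The documents give none of a, b or c, so every value below is an assumption.

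**Step 4a. Equal correlation r throughout.** The two-visit expression becomes 1 − 2r²/(1 + r).

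| r | Visit 2 only | Both visits | Ratio | Reduction |
|---|---|---|---|---|
| 0.3 | 0.910 | 0.8615 | 0.947 | 5% |
| 0.4 | 0.840 | 0.7714 | 0.918 | 8% |
| 0.5 | 0.750 | 0.6667 | 0.889 | 11% |
| 0.6 | 0.640 | 0.5500 | 0.859 | 14% |

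**Step 4b. Equal correlation, with selection at both visits.** The entry thresholds are redacted. Assume entry requires a score above the mean at both visits. Simulation with 2,000,000 draws gives ratios of 0.976, 0.941 and 0.891 at r = 0.3, 0.5 and 0.7, a reduction of about 2 to 11%.

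**Step 4c. Correlation that fades with time.** Take c = 0.6 and b = 0.5.

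- a = 0.30, which equals bc: ratio 1.000, no gain.
- a = 0.40: 1 − (0.16 + 0.25 − 0.24)/0.64 = 0.7344, and 0.7344/0.75 = 0.979, a 2% reduction.

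Now let the true level fade, with each score measured with error. Assume true correlations of 0.95 (Visit 1–Visit 2) and 0.85 (Visit 2–outcome), so 0.95 × 0.85 = 0.8075 for Visit 1–outcome.

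- Reliability 0.6: c = 0.57, b = 0.51, a = 0.4845. Both visits 0.6843, Visit 2 only 0.7399, ratio 0.925, about 7.5% lower.
- Reliability 0.8: c = 0.76, b = 0.68, a = 0.646. Both visits 0.4981, Visit 2 only 0.5376, ratio 0.926, about 7% lower.

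**Step 5. What this could mean for power.** As an illustration only, suppose an endpoint has 80% power with Visit 2 alone. The new power is Φ((1.960 + 0.8416)/√ratio − 1.960). Under equal correlation it is 82.1% at r = 0.3, 84.4% at 0.5 and 85.6% at 0.6. In the fading case with a = 0.40 it is 80.8%, and with a = 0.30 it stays at 80%.

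**Step 6. Cost if the covariate proves useless.** One degree of freedom in about 600 subjects, of the order of 1/600 = 0.17% of the information. The share is somewhat larger for conjunctival staining, which is analysed in the ITTCFS subset of undisclosed size.

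**The case against.** The strongest reply is that nothing here is wrong. ANCOVA on the last pre-treatment value is valid, keeps the type I error and matches endpoints defined as change from Visit 2. That stands: this is an optional gain in efficiency.

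The gain may also be small. The figures in Step 4a require Visit 1 to predict the outcome as well as Visit 2 does, and the design gives reasons to doubt that. At Visit 1, Section 5.4 bars eye drops only within the previous 2 hours and excludes users of topical products only if they cannot stop them. Visit 2 follows a week of vehicle. Visit 1 may therefore reflect earlier drops, which would make Visit 2 the closer predictor. This stands as a limit on size. It does not remove the expectation of some gain: under simple decay, zero gain requires Visit 2 to be measured without error, which is unlikely for a symptom score or a graded stain.

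Three stronger readings are tempting, and the documents do not support them.

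- A reader might infer that all four key secondaries would benefit. The TFBUT endpoint is a change within Visit 5, and no pre- to post-CAE pair is visible at Visit 1.
- A reader might infer that the primary and exploratory models share the gap. The primary covariates in Section 10.4.5 are redacted, and a redaction follows the model sentence in Section 10.4.7, so neither can be judged.
- A reader might take the 90% in Section 10.3 as the starting power for these endpoints. That section concerns the primary variables.

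**Conclusion.** The point holds as a free improvement, not as the correction of an error. As written, the key secondary ANCOVAs use Visit 2 alone, and for three of the four endpoints a second pre-randomisation value is scheduled and unused. Including it would probably reduce residual variance. The plausible range runs from nothing to about 14%, and the upper end needs equal correlations near 0.6 with no loss from selection at entry.

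Two assumptions carry the conclusion: the redacted scales and regions are the same at Visits 1 and 2, and Visit 1 predicts the outcome to some extent beyond Visit 2. A reader might go further and conclude that the present plan is biased, or that it will cost the trial a claim. Neither follows. The comparison is unbiased without the extra covariate, the key secondaries are formally tested only if both primaries succeed, and their power is not visible.

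**What to change.** Before unmasking, add one clause to Section 10.4.6. For Ocular Discomfort at Day 29, conjunctival fluorescein staining at Day 43 and central corneal fluorescein staining at Day 29, the ANCOVA includes as covariates both the Visit 2 baseline and the Visit 1 value of the same measure, taken from the same eye where the measure is recorded by eye. Leave the TFBUT model as it is. If the sponsor prefers Visit 2 alone, a sentence giving the reason would be enough.

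The clause should also say how a missing Visit 1 covariate is handled, so that no subject drops out of the model because of it. Such cases should be rare, since screening and run-in start at Visit 1.

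The cost is the clause and one degree of freedom per model. No new data, visits or subjects are needed.
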